2 PROTOCOL SYNOPSIS

Title A Phase 2, Randomized, Double-blind, Placebo-controlled Study of the Efficacy and Safety of VX-864 in *PiZZ* Subjects

Brief Title Evaluation of the Efficacy and Safety of VX-864 in Subjects With the *PiZZ* Genotype

[figure not shown]
Clinical Phase and Clinical Study Type Phase 2; efficacy and safety

Objectives Primary Objectives

- To evaluate the efficacy of VX-864 in *PiZZ* subjects as measured by plasma functional alpha-1 antitrypsin (AAT) levels
- To evaluate the safety and tolerability of VX-864 in *PiZZ* subjects

Secondary Objectives

- To evaluate the efficacy of VX-864 in *PiZZ* subjects as measured by plasma antigenic AAT levels
- To evaluate the pharmacokinetics (PK) of VX-864 in *PiZZ* subjects

[figure not shown]

Endpoints Primary Endpoints

- Change from baseline in plasma functional AAT levels at Day 28
- Safety and tolerability assessments based on adverse events (AEs), clinical laboratory values, standard 12-lead ECGs, vital signs, and pulse oximetry

Secondary Endpoints

- Change from baseline in plasma antigenic AAT levels at Day 28
- PK parameters of VX-864 derived from plasma concentration-time data

Number of Subjects Approximately 40 subjects with the *PiZZ* genotype

Study Population Male and female subjects 18 through 80 years of age, inclusive, with the *PiZZ* genotype

Investigational Drug Active substance: VX-864
 Activity: AAT modulator
 Strength and route of administration: 100-mg and 250-mg tablets and matching placebo for oral administration.

Study Duration Excluding the Screening Period, each subject will participate in the study for approximately 56 days: 28 days for the Treatment Period and 28 days for the Safety Follow-up Period.

[figure not shown]
Study Design This is a Phase 2, randomized, double-blind, placebo-controlled study of VX-864. Schematics of the study design are shown below.

Approximately 40 subjects in total with the *PiZZ* genotype and antigenic AAT levels <8 µM at screening will be randomized (2:1:1:1) to 1 of 3 VX-864 groups or placebo.

Of these, approximately 20 subjects will be randomized 2:2:1 to VX-864 500 mg every 12 hours (q12h), VX-864 300 mg q12h, or placebo first. The remaining subjects (approximately 20) will be randomized 2:2:1 to VX-864 500 mg q12h, VX-864 100 mg q12h, or placebo.

Randomization will be stratified by post-bronchodilator percent predicted forced expiratory volume in 1 second (ppFEV₁) obtained either during the Screening Period or from a historical post-bronchodilator ppFEV₁ value measured within 1 year before screening (<50% versus ≥50%).

[figure not shown]
Figure 2-1 Schematics of Study Design for Subjects Who Have Never Been on Augmentation Therapy

AAT: alpha-1 antitrypsin; N: number of subjects; q12h: every 12 hours
 Notes: Figure is not drawn to scale. Subject numbers include subjects who have never been on augmentation therapy and subjects who have been on augmentation therapy at any time. Antigenic AAT levels must be drawn to confirm eligibility and sent to the central laboratory; results must be obtained and confirmed to be <8 µM before randomization. Once antigenic AAT levels have been confirmed to meet this eligibility criterion, randomization and Day 1 can occur any time within the remaining screening window. **Sites should allow at least 14 days for sample processing and antigenic AAT level result reporting.**

Figure 2-2 Schematics of Study Design for Subjects Who Have Been on Augmentation Therapy at Any Time

AAT: alpha-1 antitrypsin; N: number of subjects; q12h: every 12 hours
 Notes: Figure is not drawn to scale. Subject numbers include subjects who have never been on augmentation therapy and subjects who have been on augmentation therapy at any time. Subjects must discontinue augmentation therapy >42 days before antigenic AAT levels are drawn and sent to the central laboratory to confirm eligibility; results must be confirmed to be <8 μM before randomization. Once antigenic AAT levels have been confirmed to meet this eligibility criterion, randomization and Day 1 can occur any time within the remaining screening window. Sites should allow at least 14 days for sample processing and antigenic AAT level result reporting. Subjects can resume augmentation therapy after completion of assessments at the last Safety Follow-up Visit.

*Blood samples will be obtained for antigenic and functional AAT levels at the same time that the other screening laboratory assessments are performed. If the subject received the last dose of augmentation therapy >42 days prior, this sample can be used to measure antigenic AAT level for eligibility. If samples are obtained ≤42 days after the last dose of augmentation therapy, another sample must be drawn >42 days after the last dose of augmentation therapy and sent to the central laboratory to confirm eligibility.

Assessments Efficacy:

Plasma functional and antigenic AAT levels

Safety:

AEs, clinical laboratory assessments, standard 12-lead ECGs, clinical evaluation of vital signs, pulse oximetry, spirometry, and physical examinations

Pharmacokinetics:

Plasma concentrations of VX-864

Statistical Analyses Subjects will be randomized 2:1:1:1 to receive VX-864 500 mg q12h (n = 16), VX-864 300 mg q12h (n = 8), VX-864 100 mg q12h (n = 8), or placebo (n = 8). Assuming 10% of the randomized subjects will have a missing value at Day 28, this sample size provides adequate precision to estimate the absolute plasma functional AAT levels at Day 28 for the VX-864 500 mg q12h group.

The primary endpoint to assess efficacy is the change from baseline in plasma functional AAT levels at Day 28. This primary analysis will be based on a mixed-effects model for repeated measures with change from baseline at Days 7, 14, and 28 as the dependent variable. The model will include treatment group, visit, and treatment-by-visit interaction as fixed effects. [REDACTED]

3 SCHEDULE OF ASSESSMENTS

Schedules of assessments are in Table 3-1 (Screening for subjects who have never been on augmentation therapy), Table 3-2 (Screening for subjects who have been on augmentation therapy at any time), and Table 3-3 (Treatment Period through Safety Follow-up).

Table 3-1 Study VX19-864-101: Screening for Subjects Who Have Never Been on Augmentation Therapy

Event/Assessment	Screening Period Day -35 through Day -1	Comments
Informed consent	X	Section 13.2.3
Inclusion and exclusion criteria review	X	Sections 8.1 and 8.2
Clinic visit	X	
Demographics	X	
Medical history	X	Section 11.1
Medications review	X	Section 9.6
Prior augmentation therapy review	X	Section 9.6
Antigenic AAT level	X	Antigenic AAT levels must be drawn and confirmed to be <8 μ M to establish eligibility before randomization can occur. Sites should allow at least 14 days for sample processing and antigenic AAT level result reporting. Section 8.1 , inclusion criterion #7 and Section 11.3
Functional AAT level	X	Samples will be obtained for plasma functional AAT levels at the same time samples are obtained for antigenic AAT levels. Functional AAT level results will not be provided to site personnel. Section 11.3
Standard 12-lead ECG	X	Will be performed in triplicate after the subject has rested for at least 5 minutes. When ECGs, vital signs, and blood draws are done on the same day, they should be performed in said order. Section 11.5.4
Height and weight	X	Weight and height will be measured with shoes off.
Vital signs	X	Vital signs will be performed after the subject has rested for at least 5 minutes. Section 11.5.3
Pulse oximetry	X	Pulse oximetry will be performed after the subject has rested for at least 5 minutes. Section 11.5.3
Complete physical examination	X	Section 11.5.3
Serum FSH (postmenopausal female subjects only)	X	Section 11.5.2
Serum β -hCG (all female subjects)	X	Section 11.5.2
Serology (HBsAg, HCV Ab and RNA, HIV-1 and HIV-2 Abs)	X	Section 11.5.2
PiZZ genotype	X	PiZZ genotype must be performed at the central laboratory. Section 8.1 , inclusion criterion #6
Serum chemistry	X	Section 11.5.2
Hematology	X	Section 11.5.2

Table 3-1 Study VX19-864-101: Screening for Subjects Who Have Never Been on Augmentation Therapy

Event/Assessment	Screening Period Day -35 through Day -1	Comments
Coagulation	X	Section 11.5.2
Urinalysis	X	Section 11.5.2
Spirometry	X	Spirometry will be performed post-bronchodilator and according to the American Thoracic Society Guidelines/European Respiratory Society Guidelines. If spirometry cannot be performed, historical post-bronchodilator ppFEV ₁ results measured within 1 year before screening can be used to determine eligibility. Section 8.2 exclusion criterion #7 and Section 11.5.5 .
Urine cotinine	X	Section 11.5.2
AEs and SAEs	Continuous from signing of ICF through last Safety Follow-up Visit	Section 11.5.1
Medications review	Continuous from signing of ICF through last Safety Follow-up Visit	Section 9.6

AAT: alpha-1 antitrypsin; Ab: antibody; AE: adverse event; β -hCG: beta-human chorionic gonadotropin;

FSH: follicle-stimulating hormone; HBsAg: hepatitis B surface antigen; HCV: hepatitis C virus;

HIV-1/HIV-2 Abs: antibodies against human immunodeficiency viruses 1 and 2; ICF: informed consent form;

ppFEV₁: percent predicted forced expiratory volume in 1 second; SAE: serious adverse event

Note: Screening procedures (including informed consent) can be performed over more than 1 day. Informed consent must be obtained prior to any procedures. Repeat Screening assessments and Screening assessments that were not conducted at the initial visit during the Screening Period may be performed at the clinic or at home by a qualified visiting nurse, if permitted by ethical and regulatory authorities and agreed upon after investigator and subject consultation.

Table 3-2 Study VX19-864-101: Screening for Subjects Who Have Been on Augmentation Therapy at Any Time

Event/Assessment	Screening Period Day -70 through Day -1	Comments
Informed consent	X	Section 13.2.3
Inclusion and exclusion criteria review	X	Sections 8.1 and 8.2
Clinic visit	X	
Demographics	X	
Medical history	X	Section 11.1
Medications review	X	Section 9.6
Prior augmentation therapy review	X	Subjects must discontinue augmentation therapy >42 days before the antigenic AAT levels are obtained to determine eligibility. Subjects can resume augmentation therapy after completion of the Safety Follow-up Assessments. Section 9.6
Antigenic AAT level (up to 2 samples obtained during screening)	X	Samples will be obtained for plasma antigenic AAT level and sent to the central laboratory at the same time other screening laboratory assessments are done. If the subject received the last dose of augmentation therapy >42 days prior, these results can be used to determine eligibility. If this sample is obtained ≤42 days after the last dose of augmentation therapy, another sample must be drawn >42 days after the last dose of augmentation therapy to confirm eligibility. Results must be confirmed to be <8 μM before randomization. This second sample can be drawn at a home or clinic visit. Sites should allow at least 14 days for sample processing and results reporting. Section 11.3 and Section 8.1 , inclusion criterion #7.
Functional AAT level (up to 2 samples obtained during screening)	X	Samples will be obtained for plasma functional AAT levels at the same time samples are obtained for antigenic AAT levels. If a second sample is obtained, the second sample can be drawn at a home or clinic visit. Results will not be provided to site personnel. Section 11.3
Standard 12-lead ECG	X	Will be performed in triplicate after the subject has rested for at least 5 minutes. When ECGs, vital signs, and blood draws are done on the same day, they should be performed in said order. Section 11.5.4 .
Height and weight	X	Weight and height will be measured with shoes off.
Vital signs	X	Vital signs will be performed after the subject has rested for at least 5 minutes. Section 11.5.3 .
Pulse oximetry	X	Pulse oximetry will be performed after the subject has rested for at least 5 minutes. Section 11.5.3 .
Complete physical examination	X	Section 11.5.3 .

Table 3-2 Study VX19-864-101: Screening for Subjects Who Have Been on Augmentation Therapy at Any Time

Event/Assessment	Screening Period Day -70 through Day -1	Comments
Serum FSH (postmenopausal female subjects only)	X	Section 11.5.2
Serum β -hCG (all female subjects)	X	Section 11.5.2
Serology (HBsAg, HCV Ab and RNA, HIV-1 and HIV-2 Abs)	X	Section 11.5.2
PiZZ genotype	X	PiZZ genotype must be performed at the central laboratory. Section 8.1 , inclusion criterion #6
Serum chemistry	X	Section 11.5.2
Hematology	X	Section 11.5.2
Coagulation	X	Section 11.5.2
Urinalysis	X	Section 11.5.2
Spirometry	X	Spirometry will be performed post-bronchodilator and according to the American Thoracic Society Guidelines/European Respiratory Society Guidelines. If spirometry cannot be performed, historical post-bronchodilator ppFEV ₁ results within 1 year before screening can be used to determine eligibility. Section 8.2 exclusion criterion #7 and Section 11.5.5 .
Urine cotinine	X	Section 11.5.2
AEs and SAEs	Continuous from signing of ICF through last Safety Follow-up Visit	Section 11.5.1
Medications review	Continuous from signing of ICF through last Safety Follow-up Visit	Section 9.6

AAT: alpha-1 antitrypsin; Ab: antibody; AE: adverse event; β -hCG: beta-human chorionic gonadotropin; FSH: follicle-stimulating hormone; HBsAg: hepatitis B surface antigen; HCV: hepatitis C virus; HIV-1/HIV-2 Abs: antibodies against human immunodeficiency viruses 1 and 2; ICF: informed consent form; ppFEV₁: percent predicted forced expiratory volume in 1 second; SAE: serious adverse event

Notes: Screening procedures (including informed consent) can be performed over more than 1 day. Informed consent must be obtained prior to any procedures. Repeat Screening assessments and Screening assessments that were not conducted at the initial visit during the Screening Period may be performed at the clinic or at home by a qualified visiting nurse, if permitted by ethical and regulatory authorities and agreed upon after investigator and subject consultation. If a second blood sample is required >42 days after the last dose of augmentation therapy to measure antigenic AAT levels to confirm eligibility, this second blood sample (and the second functional AAT level drawn at the same time) can be drawn at a home visit or clinic visit.

Table 3-3 Study VX19-864-101: Treatment Period and Follow-up Visits

Event/ Assessment	Treatment Period						VX-864 Washout Visit 7 (±2) Days After Last Dose of Study Drug	ETT Visit ^e	Safety Follow-up Visit 14 (±2) Days After Last Dose of Study Drug	Safety Follow-up Visit 28 (±2) Days After Last Dose of Study Drug	Comments
	Day 1 ^a	Day 7 (±1) ^b	Day 14 (±2) ^b	Day 21 (±2) ^b	Day 28 (-2) ^c						
Inclusion and exclusion criteria confirmation	X										

- ^a **On Day 1, all assessments must be completed before the first dose of study drug except for the post dose PK sampling, which is done at 3, 5, and 8 hours (±30 minutes) after dosing in the clinic.**
- ^b **All assessments will be performed before administration of the morning or evening dose of study drug unless noted otherwise (Section 11).** These visits may be performed in the morning or the evening in the clinic or at home by a qualified visiting nurse. If the visit is performed at home, it must be followed by a consultation between the subject and investigator (i.e., in person, telephone, or telemedicine video conference) within 1 day and may also include a separate follow-up with the study coordinator.
- ^c **On Day 28, all assessments will be performed before administration of the morning dose of study drug unless noted otherwise (Section 11).** The morning dose of study drug on the Day 28 Visit will be taken at home or in the clinic after the predose PK sample has been drawn (within 60 minutes of dosing). Additional PK sampling will be done at 3, 5 and 8 hours (±30 minutes) after dosing. The last dose of study drug will be taken at home in the evening on Day 28, regardless of whether the Day 28 Visit occurs on Day 26 or Day 27.

- ^e If the subject prematurely discontinues study drug treatment, an ETT Visit should be scheduled as soon as possible after the decision to terminate study treatment. Subjects who prematurely discontinue treatment will be required to complete the Safety Follow-up Visits, approximately 14 (±2) and 28 (±2) days after their last dose of study drug. If the ETT Visit occurs between 12 and 21 days (inclusive) after the last dose of study drug, the ETT Visit will replace the Safety Follow-up Visit 14 days after the last dose of study drug, and a separate Safety Follow-up Visit 14 days after the last dose will not be required; the Safety Follow-up Visit 28 days after the last dose would still be required. If the ETT Visit occurs ≥22 days after the last dose of study drug, the ETT Visit will replace the Safety Follow-up Visit 28 days after the last dose, and a separate Safety Follow-up Visit 28 days after the last dose will not be required.

Table 3-3 Study VX19-864-101: Treatment Period and Follow-up Visits

Event/ Assessment	Treatment Period					VX-864 Washout Visit 7 (±2) Days After Last Dose of Study Drug	ETT Visit ^e	Safety Follow-up Visit 14 (±2) Days After Last Dose of Study Drug	Safety Follow-up Visit 28 (±2) Days After Last Dose of Study Drug	Comments
	Day 1 ^a	Day 7 (±1) ^b	Day 14 (±2) ^b	Day 21 (±2) ^b	Day 28 (-2) ^c					
Randomization	X									Randomization may occur up to 7 days before Day 1 after all eligibility criteria including antigenic AAT levels <8 µM are confirmed. If randomization occurs before Day 1, eligibility must also be confirmed before the first dose of study drug on Day 1.
Clinic visit	X									
Clinic or home health visit		X	X	X	X	X	X	X	X	Subjects will have the option to complete these visits in the clinic or to have a home health visit. Home health visits are only an option if they receive approval from both ethical and regulatory authorities in the respective country.
Telemedicine video conference or telephone contact		X	X	X	X	X	X	X	X	Performed within 1 day after home health visit. Required only for subjects who have a home health visit; not required for subjects who have a clinic visit.
Antigenic AAT level	X	X	X		X	X	X	X	X	Section 11.3
Functional AAT level	X	X	X		X	X	X	X	X	Section 11.3

Table 3-3 Study VX19-864-101: Treatment Period and Follow-up Visits

Event/ Assessment	Treatment Period					VX-864 Washout Visit 7 (±2) Days After Last Dose of Study Drug	ETT Visit ^e	Safety Follow-up Visit 14 (±2) Days After Last Dose of Study Drug	Safety Follow-up Visit 28 (±2) Days After Last Dose of Study Drug	Comments
	Day 1 ^a	Day 7 (±1) ^b	Day 14 (±2) ^b	Day 21 (±2) ^b	Day 28 (-2) ^c					
Weight and height	X									Measured with shoes off.
Standard 12-lead ECG	X	X			X		X	X	X	Performed in triplicate after the subject has rested for at least 5 minutes When ECGs, vital signs, and blood draws are done on the same day, they should be performed in said order. Day 1: predose and 6 hours (±15 min) after dosing. Section 11.5.4
Vital signs	X	X	X		X		X	X	X	Performed after the subject has rested for at least 5 minutes. Section 11.5.3

Table 3-3 Study VX19-864-101: Treatment Period and Follow-up Visits

Event/ Assessment	Treatment Period					VX-864 Washout Visit 7 (±2) Days After Last Dose of Study Drug	ETT Visit ^e	Safety Follow-up Visit 14 (±2) Days After Last Dose of Study Drug	Safety Follow-up Visit 28 (±2) Days After Last Dose of Study Drug	Comments
	Day 1 ^a	Day 7 (±1) ^b	Day 14 (±2) ^b	Day 21 (±2) ^b	Day 28 (-2) ^c					
Pulse oximetry	X	X	X		X		X	X	X	Performed after the subject has rested for at least 5 minutes. Section 11.5.3
Pregnancy test (premenopausal female subjects of childbearing potential only)	Urine and serum		Serum		Urine		Serum	Serum	Serum	Subjects must have a negative urine pregnancy test result on Day 1 before dosing administration.
Physical examination/ review of symptoms	Abbrev PE				Review of symptoms	Review of symptoms	Review of symptoms	Review of symptoms	Review of symptoms	If there are any abnormal findings in the review of symptoms, the subject will be instructed to have a complete PE in the clinic. Section 11.5.3
Serum chemistry	X	X	X	X	X	X	X	X	X	Section 11.5.2
Hematology	X	X	X	X	X	X	X	X	X	Section 11.5.2
Coagulation	X	X	X	X	X	X	X	X	X	Section 11.5.2

Table 3-3 Study VX19-864-101: Treatment Period and Follow-up Visits

[figure not shown]
Event/ Assessment	Treatment Period					VX-864 Washout Visit 7 (±2) Days After Last Dose of Study Drug	ETT Visit ^e	Safety Follow-up Visit 14 (±2) Days After Last Dose of Study Drug	Safety Follow-up Visit 28 (±2) Days After Last Dose of Study Drug	Comments
	Day 1 ^a	Day 7 (±1) ^b	Day 14 (±2) ^b	Day 21 (±2) ^b	Day 28 (-2) ^c					
Urinalysis	X	X	X	X	X		X	X	X	Section 11.5.2
Blood for PK sampling	X	X	X	X	X	X	X	X	X	Day 1 and Day 28: predose (within 60 minutes before dosing) and at 3, 5, and 8 hours (±30 minutes) after dosing (relative to the morning dose). Days 7, 14, and 21: predose (within 60 minutes before dosing, relative to the morning or evening dose). Safety Follow-up Visits: collected at any time during the visit. Section 11.2.1
Study drug administration	Day 1 through Day 28									Section 9.7
AEs and SAEs	Continuous from signing of ICF through last Safety Follow-up Visit									Section 11.5.1
Medications review	Continuous from signing of ICF through last Safety Follow-up Visit									Section 9.6

AAT: alpha-1 antitrypsin; Abbrev: abbreviated; AE: adverse event; [REDACTED]; ETT: Early Termination of Treatment; ICF: informed consent form; [REDACTED]; PE: physical examination; [REDACTED]; PK: pharmacokinetic; SAE: serious adverse event; [REDACTED]

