11.5.4 Electrocardiograms

Standard 12-lead ECGs will be performed in triplicate. Additional standard 12-lead ECGs will be performed at any other time if clinically indicated. The performance of all ECGs will adhere to the following guidelines. Detailed instructions are provided in the Study Reference Manual:

- The ECG will be done before any other procedures that may affect heart rate, such as blood draws.
- The subject will be instructed to rest for at least 5 minutes before having an ECG.
- The test should be performed in the supine position.

A printout of the ECG traces will be made for safety review by the investigator and maintained with source documentation. Clinically significant ECG abnormalities occurring during the study through the Safety Follow-up Visit will be recorded as AEs.

To ensure safety of the subjects, a qualified individual at the study site or an approved home nurse at the home health visit will make comparisons of the QTcF value generated on the ECGs obtained at any time point after the first dose of drug administered in the treatment period to the predose baseline QTcF value taken on Day 1 in the treatment period. If the median QTcF (of the safety ECGs performed in triplicate) is increased by >60 msec from the baseline (as defined in Section 12.3.1) or an absolute median QTcF value is ≥ 500 msec for any scheduled ECG assessment, triplicate ECGs will be repeated within 10 minutes of the initial assessment to confirm the original measurement. A subject with a confirmatory ECG that demonstrates a

median QTcF (of the safety ECGs performed in triplicate) that has increased by >60 msec from the baseline or an absolute median QTcF value ≥ 500 msec will discontinue dosing. If the median QTcF (from the confirmatory ECGs repeated within 10 minutes of the initial assessment) falls below the threshold, the subject may continue dosing. If the confirmatory ECG is above the threshold then for safety monitoring, triplicate ECGs will be repeated at least every hour until the median QTcF value from 2 successive time points falls below the threshold value that triggered the repeat measurement.

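### No scheduled ECG is placed near the steady-state peak of VX-864, and Table 3-3 contradicts itself on the one post-dose ECG it does schedule

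*Protocol*

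**What the plan says.** The ECG row of Protocol Table 3-3 marks Day 1, Day 7, Day 28, the ETT Visit and the two Safety Follow-up Visits. It gives clock times for one day only: "Day 1: predose and 6 hours (±15 min) after dosing".

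Footnote b covers Day 7: "All assessments will be performed before administration of the morning or evening dose of study drug unless noted otherwise". Footnote c covers Day 28: "On Day 28, all assessments will be performed before administration of the morning dose of study drug". Both leave room for exceptions stated in Section 11. Section 11.5.4 states none for these two days. It adds ECGs when clinically indicated, and repeat triplicates once a QTcF threshold is crossed.

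The PK row reads "Day 1 and Day 28: predose (within 60 minutes before dosing) and at 3, 5, and 8 hours (±30 minutes) after dosing", so Day 28 already has three post-dose draws.

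Footnote a requires every Day 1 assessment to be finished before the first dose and exempts only the post-dose PK samples. It does not mention the 6-hour ECG.

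ECGs are part of the primary safety endpoint (Protocol 7.1). SAP 9.4.3 summarizes them by visit and time point and adds no time point of its own.

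**The concern.** Dosing is every 12 hours for 28 days. A predose ECG falls at or near trough, and the Day 1 ECG at 6 hours precedes any accumulation. If VX-864 had a concentration-related effect on QTcF, the scheduled readings would tend to understate it at the exposures subjects reach twice a day.

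The study is meant to help identify a dose for further development (Protocol 5.2). The SAP 9.4.3 summaries are what would be carried forward on QTcF, and the reader of those tables would not see that nearly all on-treatment readings were taken at low points of the dosing interval.

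The repeat-triplicate rule in 11.5.4 is also keyed to these visits, since it applies where "an absolute median QTcF value is ≥ 500 msec for any scheduled ECG assessment", or where the rise from baseline exceeds 60 msec.

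The conflict over Day 1 makes this worse. A site that follows footnote a literally would record no scheduled post-dose ECG at all.

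**Working it through.** **Step 1: count the scheduled on-treatment ECGs.**

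| Visit | Timing in Table 3-3 | Exception in Section 11.5.4 |
|---|---|---|
| Day 1 | predose and 6 h (ECG row); predose only (footnote a) | none stated |
| Day 7 | before the morning or evening dose | none stated |
| Day 28 | before the morning dose | none stated |

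Scheduled post-dose ECGs: one after the first dose (none under footnote a), and zero under repeated dosing. Post-dose PK draws on Day 28: three.

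**Step 2: how far these readings are from the steady-state peak.** The plan gives no figure to reproduce, and half-life and Tmax are not visible, so both are assumed. Model: one compartment, first-order absorption, linear kinetics, τ = 12 h.

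- ke = ln 2 / half-life; ka solves Tmax = ln(ka/ke)/(ka − ke)
- First dose: C(t) = A·[exp(−ke·t) − exp(−ka·t)], with A = ka/(ka − ke)
- Steady state: C(t) = A·[exp(−ke·t)/(1 − exp(−ke·τ)) − exp(−ka·t)/(1 − exp(−ka·τ))]
- Gap = steady-state peak ÷ the larger of (Day 1 at 6 h, steady-state trough)

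Worked case, half-life 8 h and Tmax 2 h: ke = 0.0866, ka = 1.518, A = 1.0605.

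- Day 1 at 6 h: 1.0605 × (0.5946 − 0.0001) = 0.630
- Steady-state trough: 1.0605 × 0.3536/0.6464 = 0.580
- Steady-state peak, at 1.70 h: 1.0605 × (1.3356 − 0.0762) = 1.336
- Gap: 1.336/0.630 = 2.12

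The grid used half-lives of 4, 6, 8, 12, 18 and 24 h with Tmax of 2 to 6 h in steps of 1 h. Half-life 4 h with Tmax 6 h is not attainable, because Tmax must lie below 1/ke = 5.77 h. Selected rows (gap computed before rounding):

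| Half-life, Tmax (h) | SS peak / first-dose peak | SS trough / SS peak | Day 1 6 h / SS peak | Gap |
|---|---|---|---|---|
| 4, 2 | 1.17 | 0.20 | 0.50 | 1.98 |
| 8, 2 | 1.59 | 0.43 | 0.47 | 2.12 (largest) |
| 12, 4 | 2.13 | 0.65 | 0.45 | 1.55 |
| 24, 2 | 3.47 | 0.75 | 0.26 | 1.34 |
| 24, 6 | 3.68 | 0.83 | 0.27 | 1.21 (smallest) |

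The gap runs from 1.21 to 2.12, so the best scheduled ECG sees 47% to 83% of the steady-state peak. The extremes of the other columns do not coincide: 3.68-fold accumulation goes with a trough at 83% of peak, and a trough at 20% goes with a peak only 1.17 times the first.

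**Step 3: what the existing Day 28 draws would see.** As a share of the steady-state peak: 3 h, 92% to 100%; 5 h, 68% to 99%; 8 h, 41% to 92%. The 3- and 5-hour times exceed the best scheduled ECG in every attainable combination. The 8-hour time does not when half-life is 4 h and Tmax is 2 to 4 h (for example 41% against 50%). Which draw is informative therefore depends on PK data that only the sponsor has.

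**The case against.** The strongest reply is that, on Day 7 and Day 28, nothing in the plan is inconsistent: footnotes, ECG row and 11.5.4 agree, and predose timing is a choice. The study and dose rationales (Protocol 5.2 and 9.4.3) are partly redacted, so earlier QT data may justify it. The visible text reports no QT signal. This stands, and it is why a stated justification is an acceptable answer.

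A reader might infer that QTcF is never measured near peak, or that the thresholds can act only on scheduled ECGs. The documents do not support either. Section 11.5.4 allows ECGs at any time if clinically indicated and compares QTcF from any time point after the first dose with baseline; the discontinuation sentence in 9.9 is not limited to scheduled ECGs. The ETT ECG has no fixed time relative to dose. Under 9.7 and footnote b, a Day 7 ECG can fall less than 12 hours after a dose. The finding is limited to scheduled readings.

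A reader might also pair the 3.7-fold and 20% figures; the table shows that they belong to different kinetics.

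It can be said that moving the Day 28 ECG breaks the stated order of ECG, vital signs, then blood. This is weak: the Day 1 6-hour ECG already follows the 3- and 5-hour draws. It is fair, though, that Day 28 comes too late to protect the subject much during treatment. The gain is mainly in describing the drug's effect.

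**Conclusion.** The point holds for scheduled ECGs. Under repeated dosing none is placed near the steady-state peak, and the one scheduled post-dose reading follows the first dose. Under the assumed kinetics the peak is about 1.2 to 2.1 times the highest concentration at any scheduled on-treatment ECG. That size rests on linear one-compartment behaviour, on half-life and Tmax ranges that the documents neither confirm nor exclude, and on predose readings 12 hours after the last dose. At the low end the shortfall is modest.

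The documents do not show that VX-864 prolongs QTcF, that a subject would be harmed, or that the SAP would claim a safety margin; SAP 9.4 promises descriptive summaries only.

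Separately, and without any assumption, footnote a and the ECG row contradict each other on Day 1 and must be reconciled. The change is worth making because it improves a primary safety endpoint with a procedure already scheduled.

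**What to change.** 1. Reconcile footnote a of Table 3-3 with the ECG row. If the 6-hour Day 1 ECG is intended, as the row indicates, list it beside PK sampling as an exception.
2. Either align the existing Day 28 triplicate ECG with one of that day's existing post-dose PK draws, listed as an exception to footnote c, with the sponsor choosing the draw from its own PK data, or state in the protocol why predose timing is sufficient.

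No ECG or blood draw is added, and the QTcF thresholds and stopping text are not changed. A reading taken at a draw also gives a QTcF value paired with a measured concentration; the nominal Day 1 6-hour ECG falls between the 5- and 8-hour draws.

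Cost: edits to two footnotes and the ECG row. The order of procedures at the chosen draw must be spelled out, since vital signs and the predose blood stay before the dose. If the Day 28 visit is at home, the nurse must be able to record the ECG at that time. The Day 28 ECG would no longer match the predose baseline by time of day; the Day 7 predose ECG and the placebo arm remain as references.
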